6.5. Treatment Period for Patients Treated on an Out-patient Basis

Patients treated on an out-patient basis who require hospitalisation, for whatever reason, will undergo the same procedures as patients initially treated in hospital, up to the end of the hospitalisation period, as provided for in the protocol. During this period, and up to Day 13 or Day 18, the reasons for hospitalisation will not be considered to be SAEs solely based on the criterion of hospitalisation, but may be considered to be SAEs based on other criteria (see Section 6.8.1).

PK sampling should be performed at any unscheduled visit between Day 1 and Day 10, regardless of the day on which the visit takes place.

Confidential Page 36 of 83

6.6. Procedures at the EoT Visit – Day 11

Whether the patient is being treated in hospital or as an out-patient, the following procedures will be performed at the EoT visit on Day 11:

- Collection of blood and/or lymph samples for testing for parasites;
- Collection of signs and symptoms of HAT, if any;
- Karnofsky Performance Status;
- Vital signs: body temperature, blood pressure, heart rate and respiratory rate;
- Physical and neurological examinations;
- Collection of concomitant medication and AEs;
- Urine pregnancy test for women of child-bearing potential;
- Laboratory safety assessments (see Appendix 3 Laboratory Tests; p 75) when possible, samples will be collected in the morning from patients in the fasting state;
 - Haemoglobin;
 - Haematology: WBC, platelet count;
 - o Biochemistry: albumin, ALP, ALT, AST, BUN, chloride, creatinine, glucose, potassium, sodium, calcium, total bilirubin, bicarbonates and total protein;
 - Urine analysis (leucocytes, nitrites, pH, protein, glucose, ketone bodies, urobilinogen, bilirubin, blood and haemoglobin);
- Triplicate digital ECG (CarTouch®);
- Collection of blood sample 24 hours after the last intake of the IMP (Day 11) for PK analyses. If the patient was treated on an out-patient basis, the sample will be used to check treatment compliance. If the patient was treated in hospital, a second blood sample will be collected 48 hours (Day 12) after the last intake of the IMP for PK analyses.

Table 4 - PK Sampling Times at the End of the Treatment Period

Ideal timing for sample collection	Acceptable leeway
Day 11: 24 hours after the last intake of the IMP	± 1 hour
Day 12: 48 hours after the last intake of the IMP (only for patients treated in hospital)	± 1 hour

Confidential Page 37 of 83

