## 5. ANALYSIS SETS AND SUBGROUPS

The analysis sets are the following.

- **Screened HAT positive patients:** all HAT positive patients who signed the informed consent.
- **Intent-to-treat (ITT) population:** all patients included in the study, regardless of whether or not they took the IMP (but the treatment unit was provided to the outpatient);
- **Modified intent-to-treat (mITT) population:** all patients who took at least one tablet of fexinidazole;
- **Evaluable patients:** patients included in the mITT and excluding:
  - Patients lost to follow-up at 18 months (for primary efficacy endpoint and secondary efficacy outcome at 18 month), patients lost to follow-up at 12 months (for secondary efficacy outcome at 12 month), except those who were a failure before being lost to follow-up.
  - Patients with no post-treatment lumbar puncture
  - Patients who died for reasons clearly unrelated to efficacy or safety or disease evolution (\*\*).
- **Per protocol (PP):** all patients who completed the study in accordance with the protocol with no major violations (cf. [Section 8.2](#)) that could interfere with the efficacy evaluation. An out-patient who did not take any tablet of the IMP or with a compliance below 75% of the expected number of tablets is not per protocol unless it is due to lack of tolerance. Premature withdrawal from the study due to treatment inefficacy or intolerance will not be considered as a protocol violation.

Two study cohorts are defined:

- **Inpatients:** patients treated in hospital,
- **Outpatients:** patients treated on an outpatient basis. Note that outpatients that would require hospitalization (for any reason) will be analyzed according to their initial cohort (i.e. as “outpatients”).

The following subgroups are defined according to the stage and severity of disease at inclusion:

- Stage 1
- Intermediate stage
- Stage 1 + Intermediate stage
- Stage 2
- WBC in CSF  $\leq$  100 /  $\mu$ L
- 100 < WBC in CSF  $\leq$  400 /  $\mu$ L
- WBC in CSF  $>$  400 /  $\mu$ L

For the analysis, these subgroups will be calculated as described in Table 1. Subgroups analyses are specified in [Section 8](#).

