#### 6.2.2. Compliance

As defined in the protocol, the secondary endpoints for the assessment of compliance with treatment in patients treated on an outpatient basis will be:

- Presence of fexinidazole and/or its main metabolites in the blood sample collected on Day 11 and/or at any unscheduled visit between Day 1 and the end-of-treatment (EoT) visit (*note: this endpoint will be analyzed by [REDACTED]*)
- Patients who had tablets left over at the end of treatment (i.e. number of tablets returned on day 11 > 0) (yes/no)
- Number of tablets left over at the end of treatment (i.e. number of tablets returned on day 11) (0, 1, 2, ...)
- Patients' responses to the questionnaire at the compliance interview on Day 11: Questions 5, 5.1, 5.2, 5.3 and 5.4.

In addition, the following endpoints will be assessed on all patients (i.e. inpatients and outpatients):

- Patients who completed the full course of treatment (i.e. at least 10 days) (yes/no)
- Patients fully compliant (i.e. children with body weight less than 35 kg who took exactly 14 tablets or children with body weight who took exactly 24 tablets or adults who took exactly 24 tablets) (yes/no)
- Patients who always took their treatment during a meal (yes/no)
- Patients who had at least one re-administration (yes/no)

- Patients who had at least one re-administration due to vomiting (yes/no)
- Patients who had at least one re-administration due to other reason (yes/no)
- Number of re-administration(s) by patient (0, 1, 2, ...)
- Overall compliance defined as:

- For patients with body weight < 35 kg (Children):

$$\text{Compliance (\%)} = \frac{100 \times \text{Actual dose taken (mg)}}{8400 \text{ mg (i.e. } 1200 \text{ mg} \times 4 \text{ days} + 600 \text{ mg} \times 6 \text{ days)}}$$

- For patients with body weight ≥ 35 kg (Children) or Adults:

$$\text{Compliance (\%)} = \frac{100 \times \text{Actual dose taken (mg)}}{14400 \text{ mg (i.e. } 1800 \text{ mg} \times 4 \text{ days} + 1200 \text{ mg} \times 6 \text{ days)}}$$

Note for overall compliance:

*Actual dose taken (mg) = 600 mg X number of tablets taken*

*Number of tablets taken = (sum of tablets taken from Day 1 to Day 11) + (sum of tablets taken for re-administration from D1 to D11)*

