### 6.2.3. Feasibility

As defined in the protocol, the secondary endpoints for assessment of the feasibility of self-management of treatment intake, or with the assistance of the caregiver under recommended conditions are the following for patients treated on an outpatient basis:

- Patients who temporarily discontinued their treatment (yes/no)
- Patients who prematurely (i.e. prior to Day 10) discontinued their treatment (permanent interruption) (yes/no)
- Patients who delayed starting treatment (i.e. date of D1 – date of D0 > 1 day) (yes/no)
- Patients who mislaid treatment units (i.e. number of tablets left over > 0) (yes/no)
- Patients who were hospitalized during their treatment period
- Patients with:
  - 1, 2, 3, ..., 9, 10 days of treatment administration performed at the hospital.
  - 0 days (=treatment administration performed at home only).
- Patients who took treatment regularly, according to the patients themselves (=questionnaire on Day 11: Question 5 “How did you take your treatment?”) (yes/no)
- Patients who understood the instructions concerning the dosing regimen of fexinidazole (=questionnaire on Day 0: patients who correctly answered to the 8 questions) (yes/no)
- Patients who complied with the dosing regimen, including intake of treatment during a meal (=questionnaire on Day 11: patients who correctly answered to the 4 questions 5.1 to 5.4) (yes/no)

In addition, the following data will be listed:

- Reasons of temporary treatment discontinuation
- Reasons of premature and permanent treatment discontinuation
- Reasons of hospitalization during the treatment period

The following data will also be described in patients treated in hospital:

- Patients who temporarily discontinued their treatment (yes/no)

- Patients who prematurely discontinued their treatment (permanent interruption) (yes/no)

The following data will also be listed in patients treated in hospital:

- Reasons of temporary treatment discontinuation
- Reasons of premature and permanent treatment discontinuation

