### 8.7.3. Compliance

Descriptive analyses will be provided on outpatients from the ITT population for the following endpoints:

- Presence of fexinidazole and/or its main metabolites in the blood sample collected on Day 11 and/or at any unscheduled visit between Day 1 and the end-of-treatment (EoT) visit (*note: this endpoint will be analyzed by [REDACTED]*)
- Patients who had tablets left over at the end of treatment (i.e. number of tablets returned on day 11  $>$  0) (yes/no)
- Number of tablets left over at the end of treatment (i.e. number of tablets returned on day 11) (0, 1, 2, ...)
- Patients’ responses to the questionnaire at the compliance interview on Day 11: Questions 5, 5.1, 5.2, 5.3 and 5.4.

Descriptive analyses of other endpoints listed in [Section 6.2.2](#) will be provided by cohorts, by subgroups and overall on the ITT.

Patients for whom the number of tablets taken is different from 24 (14 for children  $<$ 35 kg) or number of treatment day is different from 10 or number of tablets remaining is different from 0 or number of

re-administered tablets is different from 0 or had treatment discontinuation (permanent or temporary) will be listed with all the information concerning their treatment.

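### Out-patient compliance results count hospital-given doses in the same way as self-managed doses and are not split by place of dosing, so they can overstate adherence at home

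*SAP*

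**What the plan says.** Cohort. SAP 5 defines in-patient and out-patient cohorts and adds that "outpatients that would require hospitalization (for any reason) will be analyzed according to their initial cohort". Protocol 6.5 says that an admitted out-patient "will undergo the same procedures as patients initially treated in hospital", up to the end of the hospital stay.

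Compliance. SAP 8.7.3 introduces the four out-patient measures (Day 11 blood result, any tablets left over, number left over, interview answers) with "Descriptive analyses will be provided on outpatients from the ITT population for the following endpoints". The other measures in SAP 6.2.2, among them full course, fully compliant and overall compliance percentage, are defined for all patients and "will be provided by cohorts, by subgroups and overall on the ITT". The subgroups are stage and CSF white-cell bands. The numerator of the compliance percentage is the "sum of tablets taken from Day 1 to Day 11" plus re-administered tablets, times 600 mg. Perfect compliance (Protocol 9.6.2, repeated in SAP 8.7.3) needs drug in the blood, no tablets remaining and a credible report of full compliance.

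Feasibility. SAP 6.2.3 counts out-patients hospitalised during treatment, classifies them by the number of "days of treatment administration performed at the hospital" (1 to 10, or 0 for home only) and lists the reasons for admission. SAP 8.7.4 gives each proportion a 95% CI. Protocol 9.6.3 asks specifically for the proportion admitted for non-compliance; in the SAP this becomes any admission plus the listing of reasons.

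**The concern.** Analysis by initial cohort suits effectiveness and safety. The out-patient compliance results ask something else: whether patients or caregivers take the tablets correctly at home. Once a patient is admitted, the remaining doses say little about that, yet they enter the same numerator. The Day 11 sample is taken 24 hours after the last intake (Protocol 6.6) and serves in out-patients as a check of compliance. If the last doses were given in hospital, a positive result shows that the hospital gave them.

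At stake is how a descriptive secondary result is read. A reader of the out-patient compliance table would take it as evidence on home treatment, and nothing in that table shows how much of it rests on hospital dosing. The primary endpoint is not affected.

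**Working it through.** **1. The plan's tablet totals.** Body weight 35 kg or more: 4 × 3 + 6 × 2 = 24 tablets, and 24 × 600 = 14,400 mg. Below 35 kg: 4 × 2 + 6 × 1 = 14 tablets, and 14 × 600 = 8,400 mg. Both agree with the denominators in SAP 6.2.2 and the counts in 8.7.3. (SAP 8.5 gives 12 tablets for the lighter group. Those passages must be reconciled, but nothing here depends on it.)

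**2. Home share behind a score of 100%.** Suppose the patient takes the first *d* days at home and completes the course in hospital. The SAP formula gives 100% for every *d*. The share taken at home is:

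| Home days | 24-tablet course | 14-tablet course |
|---|---|---|
| 1 | 3/24 = 12.5% | 2/14 = 14.3% |
| 4 | 12/24 = 50.0% | 8/14 = 57.1% |
| 6 | 16/24 = 66.7% | 10/14 = 71.4% |
| 7 | 18/24 = 75.0% | 11/14 = 78.6% |

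**3. Does each measure register place of dosing?**

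| Measure | Criterion | Place of dosing used? |
|---|---|---|
| Compliance % | Tablets taken, Day 1 to 11 | No |
| Fully compliant | Exactly 24 (or 14) tablets | No |
| Full course | At least 10 days | No |
| Day 11 blood result | Drug or metabolite present | No |
| Tablets left over | Returned on Day 11 | Only if hospital doses do not come from the patient's own pack; not stated |
| Perfect compliance | Blood, leftovers, credible report | Not as a criterion |

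The individual listing in SAP 8.7.3 is triggered by tablet count, number of treatment days, leftovers, re-administration or discontinuation. Admission is not a trigger, so a patient admitted without a missed dose who completes the course is not on it.

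**4. Size, under assumptions.** Let *h* be the share of out-patients admitted, *c* the compliant share among those never admitted, and *b* the share of admitted patients who were adherent on their home days. Assume that every admitted patient completes in hospital and is scored compliant.

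- Reported rate: R = c(1 − h) + h
- Rate adherent at home: H = c(1 − h) + bh
- Overstatement: R − H = h(1 − b)

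This is 0 if b = 1 and *h* if b = 0. If b = c it is h(1 − c), which is also the excess of the pooled rate over the home-only rate *c*. With c = 90%:

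| h (assumed) | R | Excess if b = c | H if b = 0 | Excess if b = 0 |
|---|---|---|---|---|
| 2% | 90.2% | 0.2 points | 88.2% | 2 points |
| 5% | 90.5% | 0.5 points | 85.5% | 5 points |
| 10% | 91.0% | 1.0 point | 81.0% | 10 points |
| 20% | 92.0% | 2.0 points | 72.0% | 20 points |

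Over the same range of *h*, h(1 − c) runs from 0.4 to 4.0 points for c = 80% and from 0.1 to 1.0 point for c = 95%. The sign is not guaranteed in practice: an adherent patient whose treatment is stopped on admission is scored short of a full course, which pulls the other way.

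**The case against.** The strongest reply is that the plan does look at place of dosing. Self-management is the feasibility objective, and compliance is a separate one. SAP 6.2.3 and 8.7.4 report admissions, the distribution of hospital-dosed days and the home-only group, with intervals, in the same out-patient ITT population. A reader might infer that the plan hides admitted out-patients; it does not. What remains is that this variable is never crossed with compliance. Knowing that some share was admitted does not tell the reader what compliance was in the rest.

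Other parts of the reply also stand:

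- A missed dose counts as a temporary interruption and puts the patient on the SAP 8.7.3 listing. A patient admitted for non-adherence would hardly give the unquestionable report that perfect compliance requires.
- An example built on non-adherence before Day 4 would be a weak one, because Protocol 5.6.5 sends such interruptions to rescue treatment while Protocol 8.1 allows a one-day interruption. The scoring issue does not need that example: a later admission with no missed dose shows it.
- Total intake is the right quantity for the 75% per-protocol threshold and for relating outcome to tablets. On home doses alone, anyone with 6 or fewer home days would fall below 75% despite a full course.
- Admission can be for safety. Scoring every admitted patient as non-compliant would penalise adherent patients and replace one distortion with another.

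**Conclusion.** The point holds as a limited one. Out-patient compliance percentage, fully compliant, full course, Day 11 blood result and perfect compliance treat hospital-given and self-managed doses alike, so they can overstate adherence at home. The amount cannot be computed from the documents, which state neither the number of out-patients nor the share admitted nor how admitted patients behaved at home.

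If all admitted patients finish in hospital and are scored compliant, the overstatement lies between 0 and the admitted share. It is 0.2 to 2.0 points for 2% to 20% admitted, if admitted patients were 90% adherent at home like the others. A reader might infer a bias of ten points or more, but that figure simply equals the assumed admission share and requires that no admitted patient was adherent at home. Nor do the documents support reading the initial-cohort rule itself as an error. The effect on leftover tablets is open, because the source of hospital doses is not stated.

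The change is worth making because it costs little and stops hospital doses being read as home adherence.

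**What to change.** Keep the initial-cohort rule and total tablet intake for effectiveness, safety, the 75% per-protocol threshold and the models relating outcome to tablets. Then:

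1. In SAP 8.7.3, also present the out-patient compliance endpoints, the Day 11 blood result and perfect compliance separately for patients with 0 and with 1 or more hospital-administered days, using the variable already defined in SAP 6.2.3. Retain the pooled out-patient figures.
2. For admitted patients, add the compliance percentage on home-administered days: tablets taken at home over tablets due on those days. Do not automatically class admitted patients as non-compliant.
3. State whether hospital doses come from the patient's own pack, and how hospital-given tablets enter the leftover count.

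The cost is some SAP wording and one extra split, with small numbers and wide intervals in the admitted group. The home-compliance figure may be slightly less favourable. Since SAP 11 already records a change after database lock, the added tables should be labelled supplementary.

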**Table 1 : Classification of patients according to stage/severity at inclusion**

Tryps in CSF	WBC in CSF		
	≤ 5/ $\mu$ l	[6-20/ $\mu$ l]	> 20/ $\mu$ l
Tryps in CSF (positive)	Stage 2	Stage 2	Stage 2
No tryps in CSF (negative)	Stage 1	Intermediate stage	Stage 2

## 6. ENDPOINTS

### 6.1. Primary endpoint

The primary endpoint for the assessment of effectiveness will be the outcome (success or failure) at 18 months after the end of treatment. Success is defined as a cure, according to the criteria adapted from the WHO.

The outcome (success or failure) at 18 months will be calculated using the algorithm defined in [Section 10.1](#).

### 6.2. Secondary endpoints

#### 6.2.1. Intermediate endpoint at 12 months

The endpoint for an early assessment of effectiveness will be the outcome (success or failure) at 12 months after the end of treatment. Success is defined as a cure, according to the criteria adapted from the WHO.

The outcome (success or failure) at 12 months will be calculated using the algorithm defined in [Section 10.2](#).

#### 6.2.2. Compliance

As defined in the protocol, the secondary endpoints for the assessment of compliance with treatment in patients treated on an outpatient basis will be:

- Presence of fexinidazole and/or its main metabolites in the blood sample collected on Day 11 and/or at any unscheduled visit between Day 1 and the end-of-treatment (EoT) visit (*note: this endpoint will be analyzed by [REDACTED]*)
- Patients who had tablets left over at the end of treatment (i.e. number of tablets returned on day 11 > 0) (yes/no)
- Number of tablets left over at the end of treatment (i.e. number of tablets returned on day 11) (0, 1, 2, ...)
- Patients' responses to the questionnaire at the compliance interview on Day 11: Questions 5, 5.1, 5.2, 5.3 and 5.4.

In addition, the following endpoints will be assessed on all patients (i.e. inpatients and outpatients):

- Patients who completed the full course of treatment (i.e. at least 10 days) (yes/no)
- Patients fully compliant (i.e. children with body weight less than 35 kg who took exactly 14 tablets or children with body weight who took exactly 24 tablets or adults who took exactly 24 tablets) (yes/no)
- Patients who always took their treatment during a meal (yes/no)
- Patients who had at least one re-administration (yes/no)

- Patients who had at least one re-administration due to vomiting (yes/no)
- Patients who had at least one re-administration due to other reason (yes/no)
- Number of re-administration(s) by patient (0, 1, 2, ...)
- Overall compliance defined as:

- For patients with body weight < 35 kg (Children):

$$\text{Compliance (\%)} = \frac{100 \times \text{Actual dose taken (mg)}}{8400 \text{ mg (i.e. } 1200 \text{ mg} \times 4 \text{ days} + 600 \text{ mg} \times 6 \text{ days)}}$$

- For patients with body weight ≥ 35 kg (Children) or Adults:

$$\text{Compliance (\%)} = \frac{100 \times \text{Actual dose taken (mg)}}{14400 \text{ mg (i.e. } 1800 \text{ mg} \times 4 \text{ days} + 1200 \text{ mg} \times 6 \text{ days)}}$$

Note for overall compliance:

*Actual dose taken (mg) = 600 mg X number of tablets taken*

*Number of tablets taken = (sum of tablets taken from Day 1 to Day 11) + (sum of tablets taken for re-administration from D1 to D11)*

*Patients with one day delayed treatment (missing dose compensated at the end of treatment) should be considered as treatment completers. In case of death during the treatment, compliance will be calculated according to theoretical dose expected until the death.*

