1.5. Choice of the Dose and Dosing Regimen

The dose and the dosing regimen were chosen on the basis of phase-I studies in healthy volunteers. In particular, the DNDiFEX003 study demonstrated that the optimal dosing regimen should include a loading dose of 1800 mg for 4 days, followed by a maintenance dose of 1200 mg for 6 days in order to rapidly reach exposure levels in the brain at least twice as high as the minimal inhibitory concentration for M2. Use of a loading dose also leads to a shorter duration of treatment, which in turn avoids fexinidazole-related increases in liver enzyme levels. The optimal dosing regimen should also include concomitant intake of food in order to maximise exposure over a short period of time and to reduce the dose administered. Pharmacokinetic (PK) findings in adults and children included in the on-going clinical studies confirmed the dosing regimen chosen (7).

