5.1. Investigational Medicinal Product

The investigational medicinal product (IMP) is fexinidazole as 600-mg tablets, to be taken orally in a single intake during the main meal of the day at the daily dose of:

Adult patients and children with body weight equal to or above 35 kg:

- 1800 mg (3 tablets) for 4 days, followed by
- 1200 mg (2 tablets) for 6 days.

Children with body weight of at least 20 kg and below 35 kg:

- 1200 mg (2 tablets) for 4 days, followed by
- 600 mg (1 tablets) for 6 days.

The total duration of treatment will be 10 days.

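### SAP 6.2.2 scores full compliance on total tablets alone, so a course with the two dose phases reversed counts as fully compliant at 100%

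*SAP*

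**What the plan says.** **Regimen.** Protocol 5.1 sets, from 35 kg, "1800 mg (3 tablets) for 4 days, followed by" then "1200 mg (2 tablets) for 6 days". From 20 kg to below 35 kg it sets 2 tablets for 4 days, then 1 tablet for 6 days. Protocol 1.5 explains that the loading dose is used "in order to rapidly reach exposure levels in the brain" (to at least twice a stated inhibitory concentration).

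**Compliance measures.** SAP 6.2.2 first repeats the protocol's out-patient endpoints: drug in blood, tablets left over and interview answers. It then adds further endpoints for all patients. Two matter here:
- The fully compliant flag means "children with body weight less than 35 kg who took exactly 14 tablets" or, in the other band, for example "adults who took exactly 24 tablets".
- Overall compliance % has as numerator "Actual dose taken (mg) = 600 mg X number of tablets taken". The tablets are the "sum of tablets taken from Day 1 to Day 11" plus re-administered tablets. The denominator is 14400 mg or 8400 mg.

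**Per-protocol set.** SAP 5 removes an out-patient "with a compliance below 75% of the expected number of tablets", unless this is due to intolerance. It also removes patients with major violations.

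**Other checks.** Completing at least 10 days is a separate yes/no item in 6.2.2. Stopping before Day 10 is a feasibility item in 6.2.3. Day 11 questions 5 and 5.1 to 5.4 ask out-patients how they took the treatment. SAP 8.7.3 lists patients with an unexpected tablet total, a number of treatment days other than 10, left-over tablets, re-administered tablets or any discontinuation.

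**The concern.** Neither the flag nor the percentage has a term for the day, the phase or the order of intake. For a constant daily dose this would matter little. Here the regimen changes after Day 4, and the protocol gives a reason for the higher early dose. A label of fully compliant suggests that the regimen was followed, while the rule behind it shows only that the right number of tablets was used.

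This matters mainly for out-patients, who manage the change of dose themselves. Their compliance is a stated secondary objective (Protocol 2.1.2). If some take the phases in the wrong order, the reported proportion of fully compliant patients will be too high, and nothing in the tablet-based results will show it.

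**Working it through.** **Inputs.** Daily schedule: Protocol 5.1. Scoring rules: SAP 6.2.2. Listing triggers: SAP 8.7.3. Pack content: Protocol 5.3, which says that a pack holds the tablets for 10 days.

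**The plan's own totals reproduce.**
- From 35 kg: 4 × 3 + 6 × 2 = 24 tablets; 24 × 600 mg = 14400 mg.
- Below 35 kg: 4 × 2 + 6 × 1 = 14 tablets; 14 × 600 mg = 8400 mg.

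**Scoring.** Compliance % = 100 × 600 × tablets / 14400 (or / 8400). Fully compliant = total of exactly 24 (or 14). Each course is also compared day by day with the schedule. Re-administered tablets are taken as zero.

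| Course | Tablets | Compliance | Fully compliant | Days dosed | Days as scheduled | Days 1-4, taken/planned | Days 5-10, taken/planned |
|---|---|---|---|---|---|---|---|
| From 35 kg, as planned | 24 | 100% | yes | 10 | 10 | 12/12 | 12/12 |
| From 35 kg, reversed (2 × 6, then 3 × 4) | 24 | 100% | yes | 10 | 2 | 8/12 | 16/12 |
| From 35 kg, no step-down (3 × 8) | 24 | 100% | yes | 8 | 4 | 12/12 | 12/12 |
| Below 35 kg, as planned | 14 | 100% | yes | 10 | 10 | 8/8 | 6/6 |
| Below 35 kg, reversed (1 × 6, then 2 × 4) | 14 | 100% | yes | 10 | 2 | 4/8 | 10/6 |
| Below 35 kg, no step-down (2 × 7) | 14 | 100% | yes | 7 | 4 | 8/8 | 6/6 |

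In the reversed courses only Days 5 and 6 match the schedule. The dose over Days 1-4 is 8 × 600 = 4800 mg against 12 × 600 = 7200 mg planned, or 4 × 600 = 2400 mg against 8 × 600 = 4800 mg.

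**Would the SAP 8.7.3 listing show it?**
- Reversed course: total correct, 10 treatment days, nothing left over, no re-administration, no discontinuation. No trigger fires.
- No step-down: 8 or 7 treatment days, so the days trigger fires. The 10-day item is also answered no, and the item for stopping before Day 10 applies.

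**Limit of the no-step-down case.** It assumes that the patient has one pack only. A full 10 days without step-down would need 30 or 20 tablets (125% or 143%), which is more than the pack holds and would not score as fully compliant.

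**Per-protocol compliance rule.** All four deviating courses score 100%, so the 75% cut-off does not by itself exclude any of them.

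**The case against.** The strongest reply is that these are supplementary endpoints and that the plan has other safeguards. Much of this stands.

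- The planned comparison of success by compliance (Protocol 9.6.2) does not use the flag. It uses a composite of drug in blood, no left-over tablets and a credible report of full compliance. A reversed course also leaves no tablets, and with a dose on Day 10 drug would be expected in the Day 11 sample. That leaves self-report as the part likely to fail.
- SAP 6.2.3 has an out-patient item on following the dosing regimen, scored from Day 11 questions 5.1 to 5.4. Their wording is not in the documents, so they might reveal a reversed order. They change neither the flag nor the percentage.
- SAP 9.1 plans listings of treatment administration and compliance for all included patients. A reader could find a reversed course there by eye, if daily counts are shown.
- Understanding of the method of administration is a condition for out-patient treatment and is checked at dispensing. The pack mock-ups are not visible in the text, so day-by-day labelling cannot be ruled out.

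Four stronger readings are tempting, and the documents do not support them:

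- *Such patients stay in the per-protocol set.* The 75% rule is only one ground for exclusion. Under SAP 8.2 the sponsor classes violations as major or minor, and a major one excludes the patient. How a reversed or shortened course would be classed is not stated.
- *A patient who never steps down goes unnoticed.* Three other items flag that patient. Only the label is wrong.
- *Such errors are common.* No frequency is given, and nothing says which error is most likely.
- *Missing Days 1 and 2 slips past the cut-off, because 18/24 = 75.0% is not below 75%.* Day 1 is the day of first intake, so this would be a delayed start, which SAP 6.2.3 records. A total of 18 is not fully compliant and triggers the listing.

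**Conclusion.** The concern holds for the fully compliant flag and the compliance % of SAP 6.2.2. Applied as written, both give a perfect score to a 10-day course with the phases reversed, although 2 of 10 days are as scheduled and Days 1-4 hold 67% (8/12) or 50% (4/8) of the planned tablets. No 8.7.3 trigger fires. A course without step-down gets the same perfect score over 8 or 7 days, but is flagged elsewhere.

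The effect on the reported proportion cannot be sized without a frequency. The primary mITT analysis does not use these measures and is unaffected. The change is worth making because the label claims more than the rule measures, and the remedy is small.

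**What to change.** In SAP 6.2.2, define fully compliant as intake that matches the protocol's own scheduled tablet count on each treatment day. Allow the one-day shift of Protocol 8.1 by comparing the dosing days in order, and handle re-administered tablets separately. Present compliance % for Days 1-4 and for Days 5-10 beside the overall figure. In SAP 8.7.3, add to the listing any patient whose daily counts differ from the schedule.

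The daily rule is the essential part. The split percentage shows a reversed order (8/12 and 16/12, or 4/8 and 10/6) but not a missing step-down, which gives 100% in both parts.

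Before programming, the sponsor must reconcile the expected total below 35 kg, because SAP 8.5 gives 12 tablets where 6.2.2 and 8.7.3 give 14. It should also complete the second group in the 6.2.2 definition, which lacks its weight limit.

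The cost is SAP wording and a little programming, and the fully compliant proportion may fall. The summation over Days 1 to 11 implies that daily counts exist, but this is an inference because the CRF is not provided. For out-patients, such counts may rest on recall at Day 11. SAP 11 already records changes after database lock. If this is added at that stage, show it beside the existing endpoint and label it as added after lock.
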